Preventing Muscle Wasting During Rheumatoid Arthritis Flares: A Randomised Controlled Trial

335887

19.12.2023

Version 1

Preventing Muscle Wasting During Rheumatoid Arthritis Flares: A Randomised Controlled Trial

Background and Summary

This study aims to investigate aspects of muscle health changes following a disease flare-up in people with Rheumatoid Arthritis (RA) and test potential interventions to minimise any such changes.

RA is the most common inflammatory arthritis manifesting mainly as joint swelling and pain, limiting mobility, and eventually leading to loss of functional capacity. RA also has severe extra-articular manifestations (Bonfiglioli et al., 2023), affecting several tissues in the body including skeletal muscle (Farrow et al., 2021). People living with RA often present with an adverse body composition profile compared to the general population, characterised by low muscle mass at the presence of unchanged or even increased overall weight (Stavropoulos-Kalinoglou et al., 2007). This condition, termed Rheumatoid Cachexia, may affect up to 2 out of 3 people with RA and associates with active disease, further reductions in mobility, and low quality of life (Efthymiou et al., 2022).

While rheumatoid cachexia has been studied extensively, the course of its development, as well as potential causes or contributors to it are poorly understood. Inflammation, (Ollewagen et al., 2021) as well as lifestyle factors, such as energy intake, physical activity, or medication may contribute to the observed body composition changes (Masuko, 2014).

People living with RA often experience flares of disease activity, where high levels of inflammation, cause an acute exaggeration of symptoms, leading to very low levels of mobility. This is commonly treated with short-term steroid therapy which will rapidly reduce inflammation and allow the patient to regain mobility. However, that short period of high inflammatory load and low mobility may acutely affect muscle characteristics. Indeed, critically ill patients may lose up to 2% of skeletal muscle per day during the first week of hospitalisation. (Fazzini et al., 2023). This rapid decline in muscle health has been recently termed Acute sarcopenia (AS) by the European working group in sarcopenia and older persons (EWGSOP) (Cruz-Jentoft et al., 2019). Furthermore, recent work within our team is currently under review ([name] et al., 2023 *under review*) demonstrating the rapid decline of muscle mass and quality in people suffering with various diseases. Additionally, corticosteroids themselves may further contribute to muscle wasting in RA (Lemmey et al., 2018). Yet, the acute effects of flares and their treatment on muscle health in people with RA are not known.

Acute deterioration of muscle health following a flare may point towards a stepwise development of rheumatoid cachexia, i.e., bouts of acute deterioration that accumulate over time in steps rather than a continuous slow loss — which is the current understanding for the development of sarcopenia, the age-related muscle wasting. This would allow for target and potentially short-term interventions that could limit or even reverse muscle deterioration during a flare and help people with RA better maintain their functionality.

Exercise, and particularly resistance, is the most effective way to increase muscle mass, strength, and quality. However, people during and shortly after a flare may not be willing to

engage in such an intervention. Additional complexities around gym or home-based delivery, familiarisation, and safe execution render this a complex intervention with potentially limited applicability.

Nutritional supplementation on the other hand, is readily available, relatively cheap, and easy to administer. Specifically, for muscle health, amino acid supplementation, and particularly with leucine, has been shown to improve muscle mass and muscle function in older men and women (Ispoglou et al., 2016). Moreover, we have shown that amino acid supplements do not suppress appetite, are well tolerated and easy to consume. Finally, recent unpublished data from our lab suggest that amino acid concentrations in the blood following consumption alongside a meal remain elevated vs placebo for over 2 hours. This indicates that consuming two supplements per day would provide sufficient amino acids to induce beneficial effects on muscle health.

Therefore, the aims of our investigation are:

- 1. To understand the effects of acute RA flares on muscle health
- 2. To assess the efficacy of amino acid supplementation vs. standard care in maintaining muscle health.

Methodology

Participants

Eligible participants for this research study are people with rheumatoid arthritis who are experiencing a flare up of the condition. Inclusion and exclusion criteria are below.

Inclusion criteria:

RA patients who have either recently experienced a flare-up and contacted either the Rheumatology Helpline or were seen in one of the relevant clinics at Leeds Teaching Hospital Trust. The call/consultation should have occurred within the previous 4 days. Treatment for the flare may or may not have been administered already. If recruitment cannot be achieved within 4 days, we will allow up to 7 days for the baseline testing to take place before participants are no longer eligible.

Exclusion criteria:

Patients will be excluded if they present with any other comorbidity which affects muscle wasting, such as cancer or fibromyalgia, for example, or if they have had joint replacement surgery within the last 6 months. Also, patients with known or diagnosed kidney conditions will not be allowed to take part. Patients who are taking part in other research projects providing either pharmaceutical, nutritional or physical interventions will not be permitted to take part in this research project due to potential confounding variables and lack of control over participant behaviours. Patients who are pregnant will also be excluded from the study. Patients who are unable to provide their own informed consent will also be excluded. Patients who are unable to speak or understand English will also be excluded due to the need to read

and complete questionnaires written in English. Any participants who have a diagnosis of dementia or Alzheimer's disease will be excluded based on the requirement of dietary recall and remembering to take the supplement twice daily if in the intervention group. Disabled persons relying on wheelchair access will be excluded from the study due to the requirement of functional tests.

Procedure

The observation period of the research will consist of up to 5 visits to the laboratory at the Carnegie School of over a period of 3 months. Travel expenses will be reimbursed in the form of shopping vouchers from the research budget funding the study. In the event of some participants not being digitally literate and unable to receive vouchers, other means will be arranged with the participant to ensure they receive the reimbursement. The first visit to the laboratory will require the participants to recall all food and fluids consumed in the last 24 hours. Participants will be asked to refrain from strenuous physical activity 24 hours prior to each testing session and caffeine and alcohol from the evening before each testing session. Participants will also be required to arrive on all sessions having not eaten for >2 hours prior. Disease activity score will be assessed in each testing session (DAS-28).

The following schedule will be implemented throughout the period of participation and details of each session will be provided below:

- 1. First visit to Carnegie School of Sport for baseline testing (as soon as possible after flare diagnosis but no later than 7 days after)
- 2. 1-week post-baseline testing.
- 3. 2-weeks post-baseline testing.
- 4. 4 weeks post-baseline testing.
- 5. 12-weeks post baseline testing.

Participants will be randomised to either an amino acid supplement or standard care during the baseline testing session. The standard care is prescribed by the nurse at the hospital. The intervention group will be given supply for 2 supplements per day (one before breakfast and one before lunch) for a 4-week period following the baseline testing and familiarisation session. The supplements are already developed and paid for and in storage ready to use for research purposes.

Baseline Testing

Anthropometry and body composition

Height and weight will be assessed using standardised laboratory procedures and equipment including a bioelectrical impedance (BIA) machine (Seca mBCA 515 Body Composition Analyzer; a scale that also assessed body water content and estimates body composition).

Body composition will also be assessed using dual energy X-ray absorptiometry (DXA) scans. Participants will be asked to lay on the scanner with minimal clothing. DXA uses very low

intensity radiation to determine body composition and bone mineral density. It is commonly used in research and clinical practice and is considered a golden standard assessment tool for body composition and bone analysis while also being safe. Results will include information concerning lean tissue mass, fat mass, fat free mass and bone mineral density. However, only the first (baseline) and last (12-week). This takes approximately 30 minutes to complete.

Muscle mass and quality

Ultrasound (US) analysis of the quadriceps (vastus lateralis and rectus femoris) will be completed by a trained researcher and analysis will be obtained of muscle thickness, pennation angle, muscle cross-sectional area and muscle echogenicity. This will take approximately 20-30 minutes to complete. As part of the BIA assessment, this will also automatically offer another assessment of muscle quality.

Bloods

A trained phlebotomist will then take blood samples via venepuncture. 20ml of blood will be obtained in 5 tubes for subsequent assessment of:

- Amino acid content (8ml lithium heparin vacutainer tubes)
- Steroid hormone and Vitamin D content (1 x 10ml EDTA vacutainer tube)
- Erythrocyte Sedimentation Rate (2ml)

This stage will take approximately 5 minutes to complete.

Questionnaires

Participants will then be invited to relax for thirty-minutes, and enjoy a snack and a drink prior to muscle function testing, should they desire. During this break, participants will be given a series of questionnaires to complete which will offer an insight into the disease status of RA, the typical physical activity levels of the participants, the physical activity completed in the previous week, numerous diet recalls, and an overall quality of life questionnaire. The specific questionnaires included will be as follows:

- Medication Questionnaire/Record
- IPAQ (International Physical Activity Questionnaire Short)
- 24-Hour Diet Recall
- RAQoL (Rheumatoid Arthritis Quality of Life)
- PROMIS (Patient-Reported Outcomes Measurement Information System)
- MUST (Malnutrition Universal Screening Tool)

RA disease activity will be assessed by using the Disease Activity Score 28 (DAS-28) questionnaire and assessing erythrocyte sedimentation rate. This questionnaire involves the palpation of joints and whether there is any pain or tenderness.

Muscle strength and function

Muscle strength and function testing will include the following:

- Hand grip strength (HGS) using a hand-held dynamometer to assess upper-limb strength. This will be assessed on both the dominant and non-dominant side. The participant will be asked to sit down and squeeze the dynamometer as hard as possible while their elbow is flexed at 90 degrees. This will be repeated twice on each arm and the highest score will be recorded.
- Knee extensor strength (KES) using a leg extensor to assess lower limb strength. Participants will complete a submaximal strength test following a 4-6 repetition max (RM) protocol. The score achieved will be recorded and converted in to a 1RM score using a validated prediction equation (Dohoney et al., 2002). Patients will first complete a series of warm-up sets at a lower weight. The 4-6RM will be determined within 4 sets with 3-5 minutes between sets. The initial weight will represent 50% of the patients perceived 4-6RM, after which the weight will be increased by 2.5-20kg per set until the patient fails to complete the selected repetitions. The final weight lifted successfully for 4-6 repetitions will be recorded as the 4-6RM.
- Muscle function tests incorporated in the short physical performance battery (SPPB) will be conducted. These tests include the 5 times chair to stand test (CST) in which the participant will be asked to stand from a seated position 5 times and the time will be recorded, the gait speed test (GST) which will assess walking speed over a 2.44 metre distance, and a balance test. The timed up and go test (TUG) and the 6 minute walk test (6MWT) will also be performed. The TUG assess the time taken for the participant to stand up, walk around a cone 3 metres away then return to the seat and sit down. The 6MWT will be a test to see how far the participant can walk within this time frame. In the first sessions, all of these tests may not be achievable due to pain and limited mobility so we will ask participants to do them but they are able to opt out of any tests if they feel they can't complete them.

The time taken to complete the muscle function testing will vary depending on the capability of each individual, however the whole testing battery is not expected to take longer than 45 minutes.

Participants in both groups will be sent away with forms that include a weekly exercise diary, and a diet diary to be completed on 2 days per week. The intervention group will also receive a checklist which needs completing when the supplement is consumed – these only need to be completed for the 4-week intervention period following baseline testing and randomisation.

Nutritional Intervention

The oral nutritional supplement is produced using amino acids, vitamin D and flavourings, the ingredient list can be seen below:

Water, Glucose Liquid, L-Leucine, Sucrose, L-Lysine, L-Valine, Citric Acid, L-Isoleucine, L-Threonine, DLPhenylalanine, L-Hystidine (hcl), DL-Methionine, Cholecalciferol, Potassium Sorbate, Xantham Gum, Orange and Passionfruit Flavourings.

The supplement will be required to be consumed twice per day for 4 weeks. The supplement will be recommended to consume before breakfast and lunchtime meals to supplement amino acid intake at mealtimes. A checklist will be provided to the participants in this group to record their adherence to the supplement. The supplements have been used previously in older adult and clinical populations and have been well received in terms of palatability and no adverse effects have been reported deeming them safe (Older adult populations - Ispoglou et al., 2017; Multiple Sclerosis patient - Ispoglou et al., 2023; Elective and Emergency Colorectal Cancer Patients - Windle et al, https://frailty-sarcopenia.com/posters/P8.5.pdf). The supplements have also been approved for use in two previous IRAS submissions: Project ID 280595 & 222335.

All procedures outlined above will be repeated 1-, 2-, 4- and 12-weeks following baseline assessment. At each follow-up assessment, participants will also be asked about any complications relating to the study or their general health such as inability to consume the supplement, health issues, or changes to treatments etc.

[figure not shown]
In case of further flares occurring during the follow-up period, participants will be given the option to restart the study as per for the initial flare (i.e., a new baseline following the second flare, followed by 1-, 2-, 4- and 12-weeks retesting). However, if they prefer to avoid the extra testing, they will still be able to follow the original timeline for follow-up testing.

Testing sessions will be identical for participants in the amino acid supplement and standard care groups.

Schematic of visits to the testing venue and each session's testing requirements:

Testing Sessions

Randomised Groups

Group 2: Standard Care Participants in the intervention group will be given 2x supplements per day; one to consume before breakfast and one before lunch.

Randomisation to supplementation or standard care will occur at baseline testing.

Key: RA – Rheumatoid arthritis; BL – Baseline

Study Contacts:

Lead Researcher - [name]

PhD Researcher

Carnegie School of Sport,

Leeds Beckett University,

[name]

Email: [contact]

[contact]

Project Supervisor – [name]

Reader in Sports and Exercise Physiology

Carnegie School of Sport,

Leeds Beckett University,

[name]

Email: [contact]

[contact]

Project Co-supervisor – [name]

Reader in Nutrition and Muscle Health

Carnegie School of Sport,

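### Does the two-hour pre-visit eating rule leave the week 1 and week 2 blood amino acid results open to a carry-over from the last supplement drink?

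*Protocol*

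**What the plan says.** Under Procedure, the protocol sets one food rule for every visit: "Participants will also be required to arrive on all sessions having not eaten for" more than 2 hours. The other pre-visit limits concern strenuous activity, caffeine and alcohol. The supplement is not mentioned.

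The supplement is a flavoured liquid, taken twice daily for 4 weeks, "one before breakfast and one before lunch". Nutritional Intervention ties it to those meals, so that it adds to mealtime amino acid intake. The comparator is standard care, and no placebo drink is described.

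The background justifies two drinks a day with the team's unpublished observation that "amino acid concentrations in the blood following consumption alongside a meal remain elevated vs placebo for over 2 hours". It gives no upper limit.

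The amino acid sample is drawn at baseline, and all procedures are repeated at weeks 1, 2, 4 and 12. In the listed order the draw follows body composition and ultrasound. Of the ultrasound the protocol says "This will take approximately 20-30 minutes to complete", and the Bloods section then begins "A trained phlebotomist will then take blood samples via venepuncture". DXA is done only at baseline and week 12, so it adds no delay at the visits in between.

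The efficacy aim is "To assess the efficacy of amino acid supplementation vs. standard care in maintaining muscle health". The protocol gives the amino acid assay no stated role.

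**The concern.** The two figures share one bound. The food rule asks for more than 2 hours, and the rise after a drink lasts more than 2 hours with no stated end. A participant could therefore keep the rule and still be sampled while amino acids are raised by that morning's drink. Because the supplement is a liquid, a participant might also not regard it as eating at all.

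Only one arm takes a drink, so any carry-over would be one-sided. A between-arm difference at weeks 1 and 2 could then mix the effect of the last drink with a lasting change. Varying appointment times would add scatter within the supplement arm. If nobody recorded when the last drink was taken, no later analysis could separate the two. That is why the point looked like a protocol matter and not one for the analysis plan.

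**Working it through.** The protocol gives no figure to reproduce, so the check compares the timing rules and works out the gap from drink to blood draw.

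**Inputs**
- Food-free interval before arrival: more than 120 minutes (Procedure).
- Arrival to draw, *d*: 20 or 30 minutes, the ultrasound time (Muscle mass and quality). Time for weight and bioelectrical impedance is not given and would add to this.
- Drink to end of its meal, *m*: 20 or 30 minutes. This is an assumption; the protocol says only that the drink comes before the meal.
- Duration of the rise, *T*: more than 120 minutes, end unknown (Background and Summary).

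**Shortest gap in scheduled use.** The food rule runs from the end of the meal, and the drink comes earlier still. So gap = 120 + *m* + *d*:
- *m* = 20, *d* = 20: 160 minutes
- *m* = 20, *d* = 30, or *m* = 30, *d* = 20: 170 minutes
- *m* = 30, *d* = 30: 180 minutes

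Each is a minimum, before adding impedance time. If no allowance is made for the meal, the gap is 120 + 20 to 120 + 30 = 140-150 minutes plus impedance time. On either count it exceeds 120 minutes. A visit in scheduled use falls inside the rise only if the rise lasts beyond about 2.7-3.0 hours plus impedance time, and the protocol gives no evidence either way.

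**How often this could happen.** Any frequency needs clock times that the protocol does not give. Take drinks at 08:00 and 12:30 and arrivals spread evenly. The window at risk after each drink is max(0, *T* − *d* − 2 − *m*) in hours. Dividing by arrivals from 2 h + *m* to 4.5 h after each drink gives the first column. Counting all arrivals from 09:00 to 17:00, with a meal and its drink put off where needed (two windows over 8 hours), gives the second.

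| Rise lasts | Narrow set of arrivals | All arrivals 09:00-17:00 |
|---|---|---|
| 2.5 h | 0% | 0% |
| 3 h | 0-15% | 0-8% |
| 3.5 h | 25-38% | 13-21% |
| 4 h | 50-62% | 25-33% |

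For example, with *T* = 3.5 h and *m* = *d* = 20 minutes the window is 3.5 − 0.33 − 2.33 = 0.83 h. Then 0.83/2.17 = 38%, but 2 × 0.83/8 = 21%. One assumption about appointments roughly halves the answer, so these shares describe the assumptions and not the trial.

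**Visits involved.** Weeks 1 and 2 fall within the supply. For week 4, 2 × 28 = 56 drinks. If use starts on the baseline day (day 0), the last drinks fall on day 27 and the day-28 visit is clear; if it starts on day 1, the last fall on day 28, the visit day. Week 12 is off supplement. Baseline precedes it in a single-flare course; a participant who restarts after a further flare could have a new baseline soon after supplement use.

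**Records.** Questionnaires includes a 24-hour diet recall, and all procedures are repeated at each follow-up. The supplement arm also keeps a "checklist which needs completing when the supplement is consumed". The forms are not shown, so whether they record clock time is unknown.

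**The case for a change.** The best argument for acting is that the timing has to be captured on the day. If the time of the last drink is not recorded, no analysis plan can recover it, and recording it costs a sentence in the visit instructions and a few form fields. The text also leaves a case with no minimum gap: a participant who does not count the drink as eating, takes it on the way in and puts off the meal.

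Part of this stands. The rule is silent on the supplement, and a one-line clarification would do no harm. The no-gap case, however, departs from taking the drink with breakfast or lunch, and applying the background's figure to it extrapolates from data on drinks consumed alongside a meal. The irrecoverability argument assumes that the recall and the checklist lack times, which cannot be judged from forms that are not shown. Holding each participant to similar appointment times would not remove a one-sided rise, and it would burden people who may be in pain and have limited mobility.

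**Conclusion.** No change to the plan is needed. The passages do not contradict each other: the figure in the background supports two drinks a day, and the food rule is nowhere presented as a washout. The rule would be badly set only if the assay were meant to show a sustained level, and the protocol does not say so. If it serves as a marker of intake, a residual rise is what one expects to see and is not bias. How a supporting assay is interpreted commonly belongs in the analysis plan, which is not at hand.

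At its largest, the point affects one blood measure at weeks 1 and 2, and at week 4 only if the drink is still taken that day. In scheduled use the shortest gap is about 160-180 minutes plus impedance time, against a stated duration of more than 120 minutes. This rests on the listed test order and an assumed 20-30 minutes from drink to end of meal; without that allowance it is about 140-150 minutes plus impedance time. Whether any rise remains by then is unknown. The muscle-health aims are unaffected. This is a missing detail that the investigators can settle from their own data when they write the visit instructions.

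### The protocol states no masking for the reading of quadriceps ultrasound in a trial without placebo; measuring coded images in random order would supply it cheaply

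*Protocol*

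**What the plan says.** - **Comparison.** Protocol, Procedure: "Participants will be randomised to either an amino acid supplement or standard care during the baseline testing session". No placebo is described for the standard care arm. The second aim, in Background and Summary, is the efficacy of the supplement against standard care for keeping muscle health.
- **Ultrasound.** Protocol, Baseline Testing, Muscle mass and quality: two quadriceps muscles are scanned, and the protocol says that this "will be completed by a trained researcher and analysis will be obtained of muscle thickness, pennation angle, muscle cross-sectional area and muscle echogenicity". On the time needed, it adds: "This will take approximately 20-30 minutes to complete". Nothing is said about who may know the arm, about coding of images, or about the order of reading.
- **Follow-up.** Protocol, Nutritional Intervention: "All procedures outlined above will be repeated 1-, 2-, 4- and 12-weeks following baseline assessment". Each follow-up also includes questions on study complications and on matters of "general health such as inability to consume the supplement, health issues, or changes to treatments etc".
- **Timing of allocation.** Besides the sentence in Procedure, the text accompanying the schematic says "Randomisation to supplementation or standard care will occur at baseline testing".

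**The concern.** Thickness, pennation angle, cross-sectional area and echogenicity are values that a person obtains from an image. A reader who knows which participants received the supplement may, without intending it, measure in a way that favours one arm. Such a shift would add directly to the difference between arms, and a larger sample would not remove it.

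The measure is not peripheral. It is the main entry under the heading for muscle mass and quality, and it is taken at every visit, including week 4, when the supplement period ends. The DXA sentence is incomplete ("However, only the first (baseline) and last (12-week") and does not sit easily with the later statement that all procedures are repeated. If it means DXA at baseline and week 12 only, ultrasound and BIA are the only measures of muscle mass at weeks 1, 2 and 4. Of those two, ultrasound is the one that depends on a reader.

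Masking of the reading is a matter of trial conduct. An analysis plan written later cannot restore it.

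**Working it through.** The protocol gives no sample size, standard deviation, power or reading error, so there is no figure of its own to reproduce. The check is mainly a comparison of passages.

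1. **Can the arm be known?** Yes. One arm takes a product twice daily and completes a checklist, and the other does not. The only placebo mentioned (Background and Summary) belongs to earlier unpublished laboratory data.
2. **Does the measure depend on a reader?** Yes. All four parameters are attributed to the work of a trained researcher.
3. **Is it taken after allocation?** Yes, at the four follow-up visits.
4. **Could the arm come to the reader's notice?** It could. The question about taking the supplement is asked at the same four visits. The text does not say who asks it, or whether it comes before the scan.
5. **Does anything in the text prevent this?** No statement on masking, blinding, coding or concealment was found. The statement that testing sessions are identical in the two groups promises the same procedures; it does not keep an assessor unaware of the arm.

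**Illustration on assumed inputs.** This only shows why a small shift in reading would matter; none of the inputs comes from the protocol. Assume *n* per arm, a two-sided 5% test, no true effect, and a reading shift of *b* standard deviations in favour of one arm. Then, by the normal approximation,

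z = b / √(2/n), and false-positive rate = 1 − Φ(1.96 − z) + Φ(−1.96 − z).

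For n = 20 and b = 0.2: √(2/20) = 0.316, z = 0.632, and the rate is 1 − Φ(1.328) + Φ(−2.592) = 0.092 + 0.005 = 0.097.

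| n per arm | b = 0.1 | b = 0.2 | b = 0.3 |
|---|---|---|---|
| 15 | 5.9% | 8.5% | 13.0% |
| 20 | 6.2% | 9.7% | 15.8% |
| 30 | 6.7% | 12.1% | 21.3% |
| 50 | 7.9% | 17.0% | 32.3% |

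With b = 0 the rate is 5% in every row. The table is not an estimate of bias in this trial.

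**The case against.** The strongest reply is that the protocol is silent, not wrong. It nowhere says that the reader knows the arm, and the visit schematic and some pages are not in the text available. That stands, and it rules out the stronger statement, which a reader might infer, that the images are read unmasked. It does not remove the point: masking of outcome reading belongs in the protocol, and the text that describes the ultrasound procedure provides none.

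Three other inferences are tempting and are not supported.

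- **The images are read on the spot.** A reader might take this from the 20-30 minutes. The neighbouring times for DXA and venepuncture describe the visit, and the blood assays come later, so the ultrasound time most naturally means time with the participant.
- **A repeat baseline is always taken with the arm known.** After a further flare the protocol offers "a new baseline following the second flare, followed by 1-, 2-, 4- and 12-weeks retesting", on the same terms as the initial flare. It does not say whether the arm is kept or drawn again. If it is drawn again, the new allocation need not be known at that baseline. Which baseline serves as reference in the analysis may be left to an SAP.
- **The primary result is at risk.** The text available names no primary outcome, so this cannot be said.

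It is also fair to object that the remedy is narrow. Probe position and pressure during the scan, joint palpation for the DAS-28, and the strength and function tests would stay exposed. That is true, but it is no reason to leave the ultrasound reading exposed when it can be protected.

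**Conclusion.** The point holds as a cheap improvement that should be made. With no placebo and no stated masking, the plan as written leaves four reader-dependent muscle measures open to being read with the arm known at weeks 1, 2, 4 and 12, and these measures serve the second aim. Whether bias would arise, and how large it would be, cannot be derived from the protocol. The conclusion rests on the text available and on reading the trial as open because no placebo is described. If masked reading is already intended, the sponsor only needs to write it down.

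The timing of allocation is an optional clarification, not a fault. Placing randomisation at or during the baseline session does not fix the order. However, Procedure places the supplement period after baseline testing and familiarisation, and the sentence on take-home forms under Muscle strength and function names baseline testing before randomisation. Both already suggest that allocation follows the measurements.

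**What to change.** In Baseline Testing, Muscle mass and quality, add wording to this effect: *Ultrasound images are saved under codes that conceal arm and visit. After data collection is complete, the trained researcher measures all four parameters from the coded images in random order. The key to the codes stays closed until the readings are final.*

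**Cost.** Some coding work, and ultrasound results that arrive later. No extra visit, procedure or reader is needed. The change assumes that the images can be saved, which the protocol does not say. It masks the reading, but neither the acquisition of the images nor the effort-dependent tests, and the protocol should acknowledge that limit.

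**Optional.** Add one sentence in Procedure saying that the allocation is opened only after the last baseline measurement has been recorded.
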